Basis for Design of Intervention. The intervention was devised based on self-efficacy, a key concept of Social Cognitive Theory. Perceived self-efficacy is the belief that one can successfully perform a specific behavior to produce an expected outcome, and according to Bandura, stronger self-efficacy beliefs can result in greater coping efforts to overcome challenging or threatening activities.⁷⁰ CG self-efficacy has implications for both the patient and CG. In a study of 152 dyads of patients with lung cancer and their family CGs, lower levels of CG self-efficacy for pain and symptom management was significantly associated with higher levels of CG strain and mood disturbance, as well as higher levels of patient-reported pain, fatigue, anxiety, and depression, and lower levels of patient-reported quality of life.⁷¹ The proposed intervention components use strategies to strengthen self-efficacy for caregiving and self-care through *vicarious experience* (observing nurse modeling behavior during simulation), *performance accomplishments* (repeated simulation practice sessions), *verbal persuasion* (supportive nurse communication during intervention), and attention to the CG's *emotional state* (screening and intervention for emotional distress).

Basis for Study Model. The recently revised Self- and Family Management Framework,¹⁵ which acknowledges the integral role of family in managing a chronic condition, guided the conceptualization and design of this research. The framework identifies three broad **self-management processes** of “focusing on illness needs,” “activating resources,” and “living with the condition.” These processes are influenced by a complex array of **facilitators and barriers** at the individual, family, community, and healthcare system levels. The processes lead to **proximal outcomes** such as behaviors, cognitions, biomarkers, and symptom management. These proximal outcomes are mediators of more **distal outcomes** of self-management (health status, quality of life, psychosocial status, and health care). The proposed intervention specifically focuses on one component of this framework by targeting the processes for family CGs to increase self-efficacy, a cognitive proximal outcome, and to impact more distal CG outcomes.

The study model is shown in Figure 1. We posit that the intervention will work directly and indirectly (through self-efficacy) on CG outcomes. CG self-efficacy in this study is conceptualized as having two

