The Functional Assessment of Cancer Therapy - Lung (FACT-L, Version 4) is a 33-item questionnaire that measures self-reported HRQOL in patients with lung cancer over the last 7 days.^{104,105} Psychometric properties of the FACT-L were assessed by Cella et al.¹⁰⁴ in a sample of 116 patients with various types and stages of lung cancer. Internal consistency, construct validity, and sensitivity to change was established.

Interrupted Radiation Treatment Course, defined as the total number of missed treatment days due to patient or caregiver reasons, will be determined from the patient's radiation therapy treatment record. We will also record the duration (number of days) of each episode of absence from treatment.

Healthcare Utilization Outcomes

Healthcare utilization outcomes include unplanned hospital admission, unplanned emergency room visits, and unplanned IV fluid use for treatment of dehydration. We will evaluate the effects of the intervention, as compared to the control group, on these outcomes, as well as describe the costs associated with these outcomes. These outcomes will be measured at T2, T3, and T4.

Mediating Variable

Caregiver self-efficacy for caregiving will be measured with the Caregiver Inventory, a 21-item questionnaire that evaluates the domains of managing medical information, caring for the care recipient, caring for oneself, and managing difficult interactions and emotions.⁹⁹ This scale will be administered at all time points. Participants rate each item on a nine-point scale, ranging from *not at all confident* (1) to *totally confident* (9). Scores are summed, with higher scores indicating greater confidence. Psychometric properties of the Caregiver Inventory were initially reported on data from 133 family caregivers of terminally ill patients.⁹⁹ The Cronbach alpha was 0.91 and validity was supported through correlational analyses with other measures (Perceived Stress Scale and Caregiver Burden Inventory) as well as ratings by caregivers and social workers of caregiving tasks.⁹⁹

In addition, an investigator-constructed survey to measure self-efficacy for specific caregiving skills during radiation therapy will be used for descriptive purposes. Caregivers will rate their confidence in performing specific skills on a 10-point scale.

Covariates

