Analysis. This aim focuses on estimating and testing the mediating effects of family CG self-efficacy on their anxiety at Time T4 and other time points. The analysis will follow a standard (Baron-Kenny) approach of first testing the associations between intervention and the mediator (self-efficacy), and between self-efficacy and the outcome (anxiety) controlling for the intervention. If both associations are significant, the indirect effect of the mediator is estimated as the difference in the intervention effect on the anxiety before and after adjusting for the mediator.¹⁰⁹⁻¹¹¹ The standard error of the indirect effect, used to construct a confidence interval, can be estimated using a marginal regression approach with standard generalized estimating equations software, or using a bootstrap approach.¹¹¹

Power. If the effect size (difference in means of intervention vs. control groups divided by within-group standard deviation) is 0.40 for anxiety at T4, and is 0.50 for CG self-efficacy at T4 and the correlation of self-efficacy and anxiety at T4 is 0.40, the difference in means in anxiety after adjusting for the self-efficacy is reduced to an effect size of 0.20 SDs (i.e., the indirect effect of self-efficacy is 0.20, or 50% of the total). Simulations with n=10,000 replications showed in this scenario that the proposed approach had 81% power for testing that the indirect effect is zero (two-sided test, significance level 0.05). Increasing the indirect effect by increasing either the correlation or the effect of the intervention on self-efficacy results in higher power.

Aim 4

Analysis. This aim examines if patient illness factors, care demands, demographic factors, and/or use of mental health interventions during treatment moderate the relationship between the intervention and CG outcomes. Effects of potential modifiers of the treatment effect will be examined by including terms for the modifier by treatment interaction effect in the basic ANCOVA model used to test the primary hypothesis.

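### Aim 3 names no visit for the mediator, and its only stated scenario takes self-efficacy and anxiety both at T4, so a reverse link can be reported as mediation

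*Combined protocol and SAP*

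**What the plan says.** **Section 6.0, Aim 3, Analysis.** The plan tests the path from intervention to self-efficacy, then the path from self-efficacy to anxiety with the intervention in the model. Only when both tests reach significance does the plan go on, and then "the indirect effect of the mediator is estimated as the difference in the intervention effect on the anxiety before and after adjusting for the mediator". Its standard error "can be estimated using a marginal regression approach with standard generalized estimating equations software, or using a bootstrap approach". Anxiety is to be examined at T4 and at the other visits. No visit is named for self-efficacy. The text contains no lag, no baseline self-efficacy term, no reverse-direction check and no sensitivity analysis for this aim.

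**Section 6.0, Aim 3, Power.** A hypothetical scenario takes an effect size that "is 0.40 for anxiety at T4". For the mediator, the assumed value "is 0.50 for CG self-efficacy at T4 and the correlation of self-efficacy and anxiety at T4 is 0.40". From this it derives that "the indirect effect of self-efficacy is 0.20, or 50% of the total", and reports that "the proposed approach had 81% power for testing that the indirect effect is zero (two-sided test, significance level 0.05").

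**Section 1.2, Basis for Study Model.** The model is directional. The intervention is meant to "increase self-efficacy, a cognitive proximal outcome, and to impact more distal CG outcomes".

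**Sections 5.1 and 5.2, Tables 2 and 4.** Of the Caregiver Inventory, section 5.2 says: "This scale will be administered at all time points". Table 4 agrees (T1 to T4). The booster call is 2 weeks after radiation, T3 is at 4 weeks and T4 at 20 weeks.

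**The concern.** The mechanism claim needs self-efficacy to change first and anxiety to follow. Two self-reports completed at the same visit carry no information about that order: an anxious caregiver may also rate their own confidence lower that day. If the analysis follows the one scenario the plan gives, a significant indirect effect could arise when self-efficacy has no effect on anxiety at all.

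If the visit is instead left open, it can be chosen after the data are seen. In both cases the aim's conclusion, that the intervention works through self-efficacy, would not be secured by the planned analysis.

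**Working it through.** Scores are oriented so that all effects are positive. SDs are within arm and set to 1.

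**Inputs from the plan.** Anxiety effect c = 0.40; self-efficacy effect a = 0.50; same-visit correlation r = 0.40 (Aim 3 Power). T1-T4 anxiety correlation ρ14 = 0.50 (Aim 1 Power). 81 per arm (Aim 1 Power), or 107 per arm as half of the 214 in section 3.0, Projected Enrollment (equal arms assumed).

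**Assumed, not in the documents.** T1-T3 anxiety correlation ρ13 = 0.6; T3-T4 anxiety correlation ρ34 = 0.5 to 0.8; correlation q of self-efficacy residuals across visits = 0 to 0.5.

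**1. The plan's own figures.** In linear models the difference in coefficients equals a × b, where b is the slope of anxiety on self-efficacy within arm.
- Indirect effect 0.50 × 0.40 = 0.20. Share 0.20 / 0.40 = 50%. Both are reproduced.
- Power at 81 per arm by the Sobel approximation: SE² = 0.50² × 0.84/159 + 0.40² × 2/81 = 0.00132 + 0.00395, so SE = 0.0726, z = 2.75 and power is 78.7%. Simulation gives about 85% (Sobel or GEE-type) to 89% (joint test of both paths). The stated 81% lies between these, and I do not treat it as an error.

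**2. Reverse link plus a direct effect on self-efficacy.** Let anxiety drive self-efficacy with slope 0.40, and let self-efficacy have no effect on anxiety. To reach a = 0.50, the direct intervention effect on self-efficacy must be 0.50 − 0.40 × 0.40 = 0.34. The T4-T4 analysis then returns 0.50 × 0.40 = 0.20, again 50%. It is significant in 85-86% (Sobel or GEE-type) to 88-89% (joint test) of simulated trials, as under true mediation, because the joint distribution of arm, self-efficacy and anxiety at T4 is the same.

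**3. Reverse link alone.** With no direct effect, a = 0.40 × 0.40 = 0.16. The false indirect effect is 0.16 × 0.40 = 0.064, or 0.064 / 0.40 = 16% of the total. It is significant in 14% (Sobel) to 17% (joint) of trials at 81 per arm.

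**4. Case 2 with T1 anxiety and T1 self-efficacy added, mediator still at T4.** b = r(1 − ρ14²) / [r²(1 − ρ14²) + (1 − r²)(1 − q²)].
- q = 0: 0.30 / 0.96 = 0.3125; times 0.50 = 0.16.
- q = 0.5: 0.30 / 0.75 = 0.40; times 0.50 = 0.20.
- ρ14 = 0.6 and q = 0: 0.256 / 0.9424 = 0.272; times 0.50 = 0.14.

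**5. Case 2 with the mediator at T3** (true indirect effect still zero).
- No T1 terms: 0.50 × 0.40 × ρ34 = 0.20 × ρ34, so 0.10 to 0.16.
- With T1 terms: b = r(ρ34 − ρ13ρ14) / [r²(1 − ρ13²) + (1 − r²)(1 − q²)]. Low end (ρ34 = 0.5, q = 0): 0.08 / 0.9424 = 0.085; times 0.50 = 0.04. High end (ρ34 = 0.8, q = 0.5): 0.20 / 0.7324 = 0.273; times 0.50 = 0.14.
- With T3 anxiety also included: about 0, since in this model T3 self-efficacy then carries no further information on T4 anxiety.

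**6. Power with a lagged mediator** (a = 0.50, simulated Sobel test; lagged r assumed).

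| Lagged r | 81 per arm | 107 per arm |
|---|---|---|
| 0.20 | 44% | 65% |
| 0.25 | 62% | 83% |
| 0.30 | 76% | 91% |
| 0.35 | 83% | 94% |
| 0.40 | 85% | 94% |

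**The case against.** **The T4-T4 pairing is not an analysis rule.** A reader might infer that the plan prescribes it. It does not: the pairing stands only in a conditional power scenario. This stands, and the point is worded accordingly. It does not remove the problem, because the 81% is claimed for the proposed approach in that scenario and no other pairing is offered.

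**The 0.20 SD is not what a reverse link produces by itself.** A reader might infer that any anxiety-to-confidence link would be reported as 50% mediation. The documents do not support that. The figure needs the 0.34 SD direct effect on self-efficacy; without it the false effect is about 0.06 SD and usually not significant. A direct effect is plausible, since raising self-efficacy is what the intervention is built to do, but its size is an assumption. The 0.20 case shows that the two directions cannot be told apart, not how likely the reverse one is.

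**A lag is not a cure.** Step 5 shows that T3 self-efficacy without baseline terms keeps half to four-fifths of the false effect. Moving the visit alone would be an incomplete remedy.

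**The choice of lag is partly a design judgement.** T3 precedes T4 by 16 weeks. If confidence acts on anxiety quickly, the lagged effect is a different and probably smaller quantity. T2 is earlier still and, by section 5.1, falls mid-intervention. This stands. It argues for stating the choice in advance with a sensitivity analysis, not for leaving the visit open.

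**Conclusion.** The concern holds in this form: the mediator's visit is unspecified, the only stated scenario is same-visit, and a same-visit analysis cannot establish direction. A reverse link *can* be reported as mediation; it need not be.

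The size depends on whether the intervention also acts directly on self-efficacy. The false indirect effect runs from about 0.06 SD (no direct effect) to about 0.20 SD (direct effect 0.34 SD), and in the latter case T1 adjustment does not remove it. All figures assume linear relations and no effect of self-efficacy on anxiety; between-visit correlations other than the T1-T4 value are assumed.

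Reach is limited to a secondary mechanism aim. The primary comparison of anxiety at T4, the randomisation and the main sample size are unaffected.

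**What to change.** In the Aim 3 Analysis text:
- Pre-specify self-efficacy at T3 as the mediator of anxiety at T4, with T2 self-efficacy as a sensitivity analysis.
- Adjust for T1 anxiety and T1 self-efficacy.
- Add a sensitivity analysis that also adjusts for anxiety at the mediator visit.
- Report any T4-T4 result as a concurrent association.
- State that unmeasured confounding of self-efficacy and anxiety remains possible.

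In the Aim 3 Power text, replace the same-visit correlation with a stated lagged one, show a range, and use the current analysed sample.

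**Cost.** Wording only; all measures are already collected at T1 to T4. Power falls below the stated 81% if the lagged correlation is weak and only 81 per arm are analysed; at 107 per arm it is about 83% or more from a lagged correlation of 0.25 upwards. The tabulated power does not include the added baseline terms, so the restated calculation should. The lagged effect may also be smaller than a concurrent one.

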2.0 OBJECTIVES

The aims of this 2-group, prospective, randomized controlled design are:

Aim 1: Evaluate the effect of a CG intervention, as compared to a control group, on CG primary (anxiety) and secondary (depression, HRQOL, and fatigue) outcomes.

Aim 2: Measure the effect of the intervention, as compared to a control group, on patient outcomes (HRQOL and interrupted treatment course), and healthcare utilization outcomes (unplanned hospital admissions, unplanned emergency room visits, and unplanned use of intravenous [IV] fluids).

Aim 3: Determine if CG self-efficacy mediates the effect of the intervention on CG anxiety.

Aim 4: Determine if patient illness factors, care demands (hours per week spent caregiving), and patient and CG demographic factors moderate the relationship between the intervention and CG outcomes.

Aim 4a: Examine which social determinants of health (aspects of vulnerability) in caregivers moderate the efficacy of the intervention.

Aim 4b: Explore caregivers' perspectives and experiences regarding the intervention to understand how the intervention should be modified to better serve vulnerable caregivers.

Aim 5: Compare the costs of healthcare utilization (unplanned hospital admission, unplanned emergency room visits, and unplanned use of IV fluids) between the intervention and control groups.

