Patient illness factors – stage of cancer, time since diagnosis, treatment type (chemoradiotherapy vs. radiotherapy alone), HPV status (in HNC and anal cancer), use of palliative care, and patient performance status – will be recorded on the enrollment form. Updates for use of palliative care and patient performance status will be noted at T2, T3, and T4. Care demands, defined as hours/week spent caregiving, will be assessed at all time points. Demographic characteristics of both the patient and caregiver will be collected at baseline (T1). Use of mental health interventions (support group participation, social work and/or psychologist Involvement) will be assessed at all time points.

Three additional measures of social determinants of health are health insurance, social support, and financial toxicity. Health insurance will be assessed at baseline for patients and caregivers. Patient health insurance status will be obtained in the medical record, and caregiver insurance status will be obtained through self-report. Financial toxicity will be assessed with the Comprehensive Score for Financial Toxicity measure (COST), a patient-reported outcome measure that includes an 11-item scale and a single summary item of financial hardship. All items are rated on a 5-point Likert scale and lower scores indicate greater financial toxicity. The COST measure has been found to be reliable and valid in assessing caregiver financial toxicity. The 19-item Medical Outcomes Study (MOS) Social Support Survey will be used to measure perceived social support. The survey provides an overall support index score, as well as domain scores for emotional/informational, tangible, positive interaction, and affectionate support. Higher scores indicate greater support. The Ohio Opportunity Index (OOI), which measures health and well-being based on home address,

will be used to describe neighborhood characteristics for caregivers.

Other variables

Intervention dose, defined as the number of intervention sessions the caregiver receives, will be recorded at the completion of the intervention.

Other variables associated with cost analysis

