The simulation protocols were modeled after procedures used in nurse education. They contain: (1) CG learning objectives; (2) presimulation preparation, during which the intervention nurse shows the CG the manikin and reviews steps of the procedure; (3) simulation scenarios that are basic and more complex (alternative scenarios) and have a series of critical events that the CG responds to; and (4) a postsimulation debriefing during which the intervention nurse answers questions, assesses the CG's confidence in performing the skills, and provides additional training as necessary. Each simulation manual includes a structured checklist with scenarios, expected CG behaviors, and nurse prompts. Although the simulation training will follow a consistent outline, the content will be tailored to the CG's needs. CGs will have the opportunity to repeat simulations at each session. CGs will be offered a flashlight by the interventionist if they do not have one at home to use for oral assessments. An example of a simulation checklist is shown in Figure 2.

Table 3. Intervention Components

	Session One	Session Two	Session Three
Time	First 10 days of XRT	3 rd – 4 th week of XRT	Completion of XRT
Goal of session	Help CG understand the PT's experience and how to help	Review strategies for current care issues PLUS describe the typical CG experience and how the disease may affect relationship between CG and PT	Review strategies for current issues PLUS discuss common issues and concerns that may arise after cancer treatment
Content			
1. Support (Normalize concerns or experiences, listen, assess & respond to distress)	Assure CG that healthcare team will assist him/her in managing issues. -Assess CG distress & refer to SW if score \geq 5/10 -Identify resources & sources of social support for CG	-Discuss current PT issues or symptoms. -Ask, "What would you like to review today?" -Assess CG distress & refer to SW if score \geq 5/10 -Identify resources and sources of social support for CG	-Discuss current PT issues or symptoms. -Ask, "What would you like to review today?" -Assess CG distress & refer to SW if score \geq 5/10 -Identify resources and sources of social support for CG

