During the extension period, qualitative interviews will be conducted either in-person, by phone, or using UH Zoom based on caregiver preference. The interviewer will follow the interview guide, adding prompts and follow-up questions as appropriate. Interviews will last approximately 30 to 45 minutes. Interviews will be recorded and the data file will be uploaded to UH Box for storage.

Table 4. Study Measures

VARIABLE	INSTRUMENTS	TIME			
		T1	T2	T3	T4
CG Outcomes					
CG Anxiety	Patient Reported Outcomes Measurement Information System (PROMIS) ⁹⁵ Anxiety Short Form 7a	X	X	X	X
CG Depression	PROMIS ⁹⁵ Depression Short Form 8b	X	X	X	X
CG HRQOL	PROMIS ⁹⁵ Global Health Scale v.1.0/1.1	X	X	X	X
CG Fatigue	PROMIS ⁹⁵ Fatigue Short Form 7a	X	X	X	X
Patient Outcomes					
HRQOL	FACT-C, v. 4, ⁹⁶ FACT-E, v. 4, ⁹⁷ FACT-H&N, v. 4, ⁹⁸ and FACT-L, v. 4 ^{104, 105}	X	X	X	X
Interrupted radiation treatment course (total number of missed days from treatments)	Radiation Therapy PT treatment record		X		
Healthcare Utilization Outcomes					
Unplanned hospital admission	Hospital record		X	X	X
Unplanned emergency room visits	Hospital record		X	X	X
Unplanned intravenous fluid use	Hospital record (number of liter bags used)		X	X	X
Cognitive Mediator					
CG self-efficacy for caregiving	CG Inventory ⁹⁹	X	X	X	X
	Investigator-constructed self-efficacy scale for managing side effects & specific skills	X	X	X	X
Potential Moderators (Covariates)					
Patient Illness Factors (Stage; time since diagnosis; treatment type, e.g., concurrent chemotherapy; HPV status in HNC and anal cancer)	PT medical record	X			
Use of palliative care services	PT medical record	X	X	X	X
PT Performance Status	ECOG Performance Status ^{100,101} (patient)	X	X	X	X
Care Demands (hours/week spent caregiving)	Interview questions (CG)	X	X	X	X
Demographic characteristics (race, marital status, employment status, health insurance, socioeconomic status)	Interview questions (CG and PT)	X			
Use of mental health interventions (support group participation, social work and/or psychologist involvement)	Interview questions (CG and PT)	X	X	X	X
Financial toxicity	COST-FACIT (version 2)		X		X
Social support	MOS		X		

Note. PT = Patient; CG = Caregiver; ECOG = Eastern Cooperative Oncology Group; ADLs = Activities of daily living. CG age, CG gender, and PT cancer type will be used in the minimization stratified randomization technique. Number/types of care demands will be collected as descriptive data.

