Power. Analyses for Aim 4 to examine moderating effects will be primarily exploratory in nature, since it is well-recognized that power for testing interaction effects is not high in trials that are powered to detect main effects, as is the case here.¹¹² When testing interaction of a binary factor occurring with frequency 0.5, power is 0.86 to detect an interactive effect size of 1.0 SDs (e.g., an intervention effect of 1.0 in one subgroup and an effect of 0.0 in the other), using a 2-sided test, significance level 0.05.

Aim 4a: Analyses for Aim 4a will examine if the SDH variables moderate the relationship between the intervention and caregiver outcomes. Effects of potential modifiers of the treatment effect will be examined by including terms for the SDH modifier by treatment interaction effect in the basic ANCOVA model used to test the primary hypothesis. The increase in enrollment from the extension study will provide additional power, as it is well-recognized that power for testing interaction effects is not high in trials that are powered to detect main effects, as was the case with the parent study. When testing interaction of a continuous SDH modifiers and the treatment, power is 0.81 to detect an interactive effect size of 0.40 standard deviations (SD) using a 2-sided test, significance level 0.05, for those measures that will be available in all subjects (e.g. Ohio Opportunity Index). For SDH measures that will only be available in the 96 extension study participants, we will be able to detect an interactive effect size of 0.59 at the same power and significance levels.

Aim 4b: Qualitative interviews will be audio recorded and transcribed, then verified for accuracy by research staff. Any identifiable information will be removed from transcripts, and each will be assigned a

study number. Deidentified data will be analyzed with NVIVO software using thematic analysis. First, the research team, including the PI, will read and reread 5 transcripts to develop a codebook using an inductive approach. Then, all transcripts will be coded by the research team using NVIVO to organize the data. Additional codes, and subsequently categories of codes will be identified. Clusters of categories converged into themes. Each transcript will be read and coded by three members of the research team for interrater reliability.

Aim 5

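### Aim 4a tests financial toxicity and social support as treatment-effect modifiers, but both are first measured after randomisation, so their interactions cannot be read as baseline effect modification without an assumption the plan does not state

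*Combined protocol and SAP*

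**What the plan says.** Section 2.0 sets Aim 4a: "Examine which social determinants of health (aspects of vulnerability) in caregivers moderate the efficacy of the intervention". Section 6.0 carries it out by "including terms for the SDH modifier by treatment interaction effect" in the ANCOVA model used for the primary hypothesis. It states power 0.81 (two-sided 0.05) for an interaction of 0.40 SD with measures held on all subjects, and the same power for 0.59 SD with measures held only on the 96 extension participants.

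Section 5.2 (Covariates) says: "Three additional measures of social determinants of health are health insurance, social support, and financial toxicity". It gives a time point for the first only: "Health insurance will be assessed at baseline for patients and caregivers". It adds the Ohio Opportunity Index, which rests on home address.

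Table 4 (section 5.4) places COST and MOS under "Potential Moderators (Covariates)". The row "COST-FACIT (version 2)" is marked at T2 and T4, and the row "Social support MOS" at T2 only. Neither has a T1 mark.

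Section 4.0 places randomisation after the baseline data. In section 5.1, T2 is the end of radiation. In Table 3 (section 5.3), session 1 falls in the first 10 days, session 2 in week 3 or 4, and session 3 at completion of radiation. The support content of all three sessions includes the item "Identify resources and sources of social support for CG" (session 1 words it almost identically).

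**The concern.** A modifier-by-treatment interaction answers the Aim 4a question, which existing vulnerabilities change the benefit, when the modifier is fixed before allocation. A score taken at T2 need not be. If the sessions help some caregivers find support, those caregivers count as better supported because they were treated, and a given MOS score then describes different people in the two arms.

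Two errors can follow. True baseline moderation can be diluted, because the T2 score is an imperfect stand-in for the T1 score. Alternatively, an interaction can appear with no baseline moderation, because the caregivers whose support improved are also those whose anxiety improved. A T4 COST score is further removed: it is taken after every intervention contact and at the same visit as the primary outcome. At stake is any conclusion about which vulnerable caregivers the intervention serves well or poorly.

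**Working it through.** **Timing.** The columns of Table 4 can be checked against the text. Healthcare utilisation rows start in the T2 column, and section 5.2 says those outcomes are measured at T2, T3 and T4. Demographics are marked in the T1 column, and section 5.2 says T1. So the empty T1 cells for COST and MOS are consistent with the rest of the table. The order is T1, randomisation, session 1, session 2, then T2, with session 3 at about the same time as T2 and the booster call two weeks later. No section gives a baseline COST or MOS, says which COST time point enters the model, or discusses the timing.

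**The plan's own figure.** For a standardised continuous modifier, equal arms and residual SD 1, the SE of the interaction slope is 2/√N.
- N = 96, effect 0.59: SE = 2/√96 = 0.204; 0.59/0.204 = 2.89; power = Φ(2.89 − 1.96) = 0.82. The noncentral t also gives 0.82. Stated: 0.81.
- N = 214, effect 0.40: SE = 2/√214 = 0.137; 0.40/0.137 = 2.93; power = 0.83. Stated: 0.81.

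The stated figures reproduce closely for a modifier fixed before allocation. Simulation with a randomly drawn modifier gives about 0.80 at N = 96, the reference used below.

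**Illustration 1, dilution.** Assumed: N = 96, true interaction 0.59 SD with the T1 score, a T2 score unaffected by arm, and T1-T2 correlation r. The slope on the T2 score is 0.59 × r.
- r = 0.6: slope 0.35, simulated power about 0.37
- r = 0.7: slope 0.41, simulated power about 0.46
- r = 0.8: slope 0.47, simulated power about 0.57

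Keeping the SE at 0.204 would give somewhat higher power, but the part of the baseline interaction that the T2 score misses adds variance in the treated arm. At r = 0.7 that arm's residual variance is 1 + 0.59² × (1 − 0.49) = 1.18, so SE = √((1 + 1.18)/48) = 0.213 and power = Φ(0.413/0.213 − 1.96) = 0.49. Simulation, which also lets the modifier vary, gives about 0.46.

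**Illustration 2, spurious interaction.** Assumed: no baseline moderation and r = 0.7 in controls. Among treated caregivers, a latent engagement variable (SD 1) raises the T2 score by g SD and lowers anxiety by b SD per unit. The interaction expected on the T2 score is −gb/(1 + g²).
- g = b = 0.3: −0.09/1.09 = −0.08; simulated type I error about 7%
- g = 0.5, b = 0.4: −0.20/1.25 = −0.16; about 12%
- g = b = 0.5: −0.25/1.25 = −0.20; about 15%

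These are for N = 84 to 96, the extension sample with the plan's 12% dropout (96 × 0.88 = 84) and without it. Using the T1 score in the same data gives about 5%. At g = b = 0.2 the T2 score also gives about 5%.

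**The case against.** The strongest reply is that a T2 score may be a serviceable proxy. If support and financial strain are stable over six to eight weeks and do not respond to the intervention, little is lost. That is possible, so it would go too far to infer that these interactions can say nothing about who benefits. But the proxy needs an assumption that the plan neither states nor tests, and for MOS the session content argues against taking it for granted.

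The case is weaker for COST. The session link is information on financial and work issues in session 3, which falls at about the time of T2. Section 5.2 also anticipates travel expenses for meeting the intervention nurse. Either could move the score, but nothing shows that it would by T2.

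A reader might also infer that half of the SDH measures, or the whole sub-aim, are compromised. The documents do not support that. Section 5.2 calls insurance, support and financial toxicity additional measures, and Table 4 collects race, marital status, employment, insurance and socioeconomic status at T1. The Ohio Opportunity Index depends on address.

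Section 6.0 labels the Aim 4 analyses primarily exploratory. This tempers the severity, but it is offered as a reason for low power and does not address when a moderator is measured. Aim 4a also has its own power statement.

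Finally, n = 96 for COST and MOS is an inference. The plan does not say they are the extension-only measures, and the amendment log adds them in April 2022, before the extension changes of December 2022. The available number may be larger.

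**Conclusion.** The point stands, limited to COST and MOS. Table 4 schedules both only after allocation and at least two intervention sessions, while Aim 4a treats SDH measures as effect modifiers. Their interactions with arm are therefore not baseline effect modification unless the scores are stable and unaffected by arm. An arm effect is plausible for MOS, and possible but less supported for COST.

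The timing finding needs no assumed figure. The size does: the correlations, g and b are not in the documents, and n = 96 is inferred. On those values the loss ranges from moderate to large (power about 0.57 down to 0.37, against about 0.80), and type I error from near nominal to about 15%. These are illustrations, not estimates for this trial. Nothing here touches the primary endpoint, the allocation or the Aim 1 test, and it should not be read as a criticism of Aim 4a's baseline or address-based moderators.

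**What to change.** - State in Aim 4a that every moderator is defined by its pre-randomisation value.
- Limit effect-modification claims to SDH measures fixed or collected before randomisation: the Ohio Opportunity Index, insurance and T1 demographics.
- Report results for T2 or T4 COST and MOS as associations, not moderation, and name the COST time point used.
- If any caregivers are still to be enrolled, add COST and MOS at T1 before allocation, and keep the T2 administration so that they remain comparable with caregivers already measured.

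The first three changes are a few sentences and need no new data. The fourth adds about 31 items to the T1 survey (COST 11 + 1, MOS 19). It may come too late: the extension planned 16 months of enrolment after the December 2022 amendment, which points to about April 2024, and the log runs to March 2025. If enrolment is advanced or complete, few or no caregivers will have a valid COST or MOS moderator, and Aim 4a must rest on the remaining SDH measures.
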